1.0 PROTOCOL SUMMARY

1.1 Synopsis

Protocol Title:

A Phase 1a, Randomized, Double-Blind, Placebo-Controlled, Single Center Study to Evaluate the Safety, Tolerability, and Pharmacokinetics of CS-1103 Following Single, Ascending Intravenous Dose Administration in Healthy Participants

Registry **ID:** IND 155105

Principal Investigator: [name]., FCCP, FAASM

Indication: To lower the level of methamphetamine in the human body

Rationale:

The purpose of the study is to evaluate safety, tolerability, and pharmacokinetics (PK) of single, ascending doses of CS-1103, administered by intravenous (IV) infusion in healthy participants.

Objectives and Endpoints

Objectives	Endpoints
Primary	

To assess the safety and tolerability of CS-1103, administered by IV infusion	Standard safety and tolerability parameters but not limited to: 
AEsVital signs (blood pressure, pulse rate, respiratory rate, oxygen saturation, and body temperature)Digital 12-lead ECGs/HolterLaboratory parameters (clinical chemistry, hematology, coagulation, urinalysis)
Secondary	Plasma and urine PK parameters including but not limited to: 
C_{max}, t_{max}, C_{EOI}, $AUC_{(0-last)}$, $AUC_{(0-inf)}$, $t_{1/2}$, λ_z, CL, V_{ss}, and V_zBy-interval and cumulative CS-1103 excretion in urine (A_e and f_e)CL_r

Exploratory	

 To explore the relationship between CS-1103 plasma concentrations and changes in QT intervals during dosing, if any 	
 Concentration-QT correlation performed on baseline-corrected QTcF time-matched with PK. Concentration-QT correlation may be reported separately from the clinical study report

Abbreviations: AE = adverse event; A_e = amount; AUC = area under the concentration versus time curve; AUC_(0-inf) = AUC from time zero extrapolated to infinity; AUC_(0-last) = AUC from time zero to the last quantifiable concentration; C_{EOI} = concentration at the end of 10-minute IV infusion; CL = systematic clearance; CL_r = renal clearance; C_{max} = maximum concentration; ECG = electrocardiogram; f_e = fraction; IV = intravenous; λ_z = elimination rate constant; PK = pharmacokinetics; t_{1/2} = half-life; QTcF = QT corrected for heart rate by Fridericia's formula; t_{max} = time to C_{max}; V_{ss} = volume of distribution at steady-state following intravenous dosing; V_z = volume of distribution following intravenous dosing.

Overall Design:

CS-1103-01 is a Phase 1a, single center, double-blind, placebo-controlled, randomized, single ascending-dose first in-human (FIH) study. All participants will be screened within 28 days of dose administration and participants will check-in to the inpatient clinical research unit (CRU) on their Admission/Day -1. Participants will be randomized on Day -1, the day prior to dosing, after meeting all eligibility criteria. Participants are scheduled to remain in the CRU for up to 48 hours postdose for safety and PK assessments.

Number of Participants:

Up to 40 healthy participants, aged 18 to 55 years will be randomized.

Intervention Cohorts and Duration:

Up to 5 cohorts of 8 participants (6 active, 2 placebo participants per cohort) will be enrolled with each participant assigned to receive a single dose of CS-1103 or placebo on 1 occasion (Day 1). Note: The dose will be capped at 3000 mg.

- Cohort 1: Dose level 1 (CS-1103 2.7 mg/kg, [REDACTED] or placebo [REDACTED])
- Cohort 2: Dose level 2 (CS-1103 8.0 mg/kg, [REDACTED] or placebo [REDACTED])
- Cohort 3: Dose level 3 (CS-1103 16.0 mg/kg, [REDACTED] or placebo [REDACTED])
- Cohort 4: Dose level 4 (CS-1103 26.7 mg/kg, [REDACTED] or placebo [REDACTED])
- Cohort 5: Dose level 5 (CS-1103 40.0 mg/kg, [REDACTED] or placebo [REDACTED])

The study duration will be approximately 37 days.

- Screening Period: up to 28 days
- CRU confinement period: 4 days
 - Treatment administration: 1 day
- CRU discharge through follow-up/end of study period: 5 days

Statistical Methods:

Descriptive statistics will be used as applicable to summarize the study data unless otherwise specified. Continuous variables: Sample size (n), mean, standard deviation (SD), median,

minimum (min), and maximum (max). Summaries for plasma CS-1103 concentrations will include the coefficient of variation and PK parameter summaries will also include the geometric mean (except for t_{max} , which will only be presented as min, median, max). Categorical variables: Frequencies and percentages. Individual participant data will be presented in listings.

The sample size for this study is based upon precedent set by other Phase 1 studies to gain preliminary measure of safety and CS-1103 PK characteristics in a healthy participant population and not on statistical considerations of power while exposing as few participants as possible to the study treatment and procedures. A sample size of 8 participants per dose level (6 active: 2 placebo) in this study design is expected to be sufficient to meet the objectives of this study.

Safety:

Analysis of safety data will be performed for all participants receiving at least one dose of study treatment (CS-1103 or placebo). The frequency of all treatment emergent adverse events (TEAEs), TEAEs by maximum severity, TEAEs by relationship to study treatment, serious adverse events (SAEs), TEAEs leading to death, and TEAEs leading to discontinuation of study treatment will be tabulated by Preferred Term (PT) and System Organ Class (SOC) for each treatment cohort. Summary statistics, including change from baseline, for vital signs, laboratory parameters, and electrocardiograms (ECGs) intervals will be provided by treatment, visit, and time point, as appropriate. For ECG results, appropriate outlier tabulations for QT and QT corrected for heart rate by Fridericia's formula (QTcF) will also be presented by treatment. Results of the physical examinations and the Anxiety Symptoms Questionnaire (AQS) will be listed and if appropriate, summarized by treatment.

Pharmacokinetics:

[figure not shown]
Analysis of PK data will be performed for all participants receiving at least one dose of CS-1103 and have at least 1 quantifiable postdose concentration, without protocol deviations or events expected to affect PK results. CS-1103 concentrations and calculated PK parameters will be listed and descriptively summarized by treatment and scheduled time point, as applicable. Arithmetic mean \pm SD and individual CS-1103 plasma concentration versus time curves will be plotted on linear and semilogarithmic scale and percent of dose recovered in urine over time will be presented graphically, as appropriate. Dose proportionality will be explored graphically and by using a power model, as appropriate.

Data Monitoring/Other Committee: Yes

Dose escalation, and other decisions related to safety and PK will be made by the Sponsor in consultation with a Safety Review Committee (SRC).

1.2 Schema

Figure 1 Study Schema

Abbreviations: CRU = clinical research unit; EOS = end of study, IV = intravenous.

Up to 40 participants randomized to 5 cohorts of 8 participants each (6 active, 2 placebo participants per cohort). Note: Admission/Day -1 may span 2 days in the CRU, in that case screening will end on Day -3 for participants with Admission Day spanning 2 days in the CRU.

1.3 Schedule of Activities

Table 3 Schedule of Activities

Visit type:	Screening ^a	Admission to CRU ^a	In-CRU	In-CRU	Discharge	Follow-up/ EOS ^b
Procedure:	-28 to -2	Admission/ Day -1	Day 1	Day 2	Day 3	Day 8 ±1 day
Informed Consent	X					
Demographics	X					
Medical History	X					
COVID-19 test ^c		X				
Drug of Abuse/Alcohol Screen	X	X				
HIV/HBsAg/HCV Serology	X					
FSH (females only)	X					
Serum Pregnancy Test (females only)	X					
Urine Pregnancy Test (females only)		X				X
Weight; Height/BMI (screening only)	X	X				X
Inclusion/Exclusion criteria	X	X				
Previous/Concomitant Medications ^d	X	X	X	X	X	X
Clinical Laboratory Evaluations ^e	X	X	X ^e	X		X
Safety ECG ^f	X	X	X	X	X	X
Holter Monitoring ^{g,h}		X ^g	X ^h	X ^h		
Vital Signs ⁱ	X	X	X	X	X	X
Physical Examinations ^j	X	X		X	X	X
Injection Site Assessment ^k			X	X	X	
ASQ ^l	X	X	X			
AE/SAE events ^m	X	X	X	X	X	X
Randomization		X				
Administer Dose in-CRU ⁿ			X			
PK Blood Samples ^o			X	X	X	
Pooled Urine Collection ^o		X	X	X	X	

Abbreviations: AE = adverse event; ASQ = Anxiety Symptoms Questionnaire; BMI = body mass index; COVID-19 = coronavirus disease 2019; CRU = clinical research unit; ECG = electrocardiogram; EOS = end of study; FSH = follicle stimulating hormone; HBsAg = Hepatitis B surface antigen; HCV = hepatitis C virus; HIV = human immunodeficiency virus; ICF = informed consent form; IV = intravenous; PK = pharmacokinetic; SAE = serious adverse event; SoA = schedule of activities.

- a. All participants within a given cohort may check-in on the day prior to sentinel dosing and remain confined to the study center until their discharge day. Two participants will be randomized for dosing in the sentinel group, and the remaining participants may be eligible to participate in the main cohort group without repeating the admission evaluations, provided they were in confinement the entire time. The remaining participants will have a set of vital signs and AE/concomitant medication review performed on the day prior to their dosing day. For remaining participants, Admission/Day -1 may span 2 days in the CRU. Note: Screening may end on Day -3 for participants with Admission Day spanning 2 days in the CRU.
- b. Participants who discontinue from the study prematurely should perform the Follow-up/EOS Visit as soon as possible after discontinuation.
- c. A COVID-19 test will be performed at Admission and for which a negative result must be available prior to study treatment administration.
- d. Includes over-the-counter medications, herbal medications/supplements, and other supplements.
- e. Clinical laboratory tests: hematology, clinical chemistry (including liver and renal function), coagulation, and urinalysis with microscopic examination to be performed at screening, on Admission/Day -1, Day 2 and EOS. In addition, urinalysis will be performed for each urine sample collected on Day 1. Protocol-required laboratory tests are detailed in [Section 10.2, Table 6](#).
- f. Triplicate 12-lead ECGs will be obtained following at least 5 minutes remaining in a supine position and collected before other simultaneously scheduled procedures, i.e., vital signs and blood collections. Single ECGs may be collected during the first 30 minutes post-EOI to allow completion of all simultaneously scheduled procedures (see [Table 2](#)).
- g. On Admission/Day -1, continuous Holter Monitoring will be performed for 4 hours. If needed, any repeat ECG needs to be performed in triplicate.
- h. On Day 1, continuous Holter Monitoring will commence approximately 1 hour prior to study treatment administration and continue through 24 hours postdose. The ECGs will be extracted from Holter to be time-matched with PK samples (see [Table 2](#)).
- i. Vital signs (Systolic, diastolic, and mean blood pressure, pulse rate, respiratory rate, oxygen saturation, and body temperature) will be measured following at least 5 minutes remaining in a supine position following ECG collection (see [Table 2](#) and [Section 8.2.2](#) for details). If needed, repeat vital signs may be performed.
- j. Complete physical examination at screening and at end of study. Brief physical examination on Admission/Day -1 at check-in, Day 2, and Day 3.
- k. On Day 1, the injection site will be evaluated prior to study treatment administration and again immediately after study treatment administration, in approximately (+15 minutes) hourly intervals for up to 6 hours postdose. Injection site assessment also occurs any time on Day 2, and any time prior to discharge from the CRU on Day 3. (see [Section 8.2.1.1](#) for details on the 4-point scale injection site assessment).
- l. On Day 1, ASQ will be completed predose (within 60 minutes prior to dosing) and approximately 10 minutes (+15 minutes), 1 hour (+15 minutes), and 2 hours (+15 minutes) postdose. This assessment will be performed after completion of all other simultaneously scheduled procedures to avoid interference with scheduled vital sign, ECG, and PK evaluation (see [Section 8.2.4](#)).
- m. All SAEs will be collected from the signing of the ICF until the last study visit at the timepoints specified in the SoA. All AEs will be collected from the start of study treatment until the last study visit at the timepoints specified in the SoA.
- n. Study Treatment will be administered on Day 1 in the morning after at least a 10 hour overnight fast with an approximately 4 hour fast following dose administration. Note: All scheduled postdose assessments listed in [Table 1](#) and [Table 2](#) are relative to the start of the IV infusion.
- o. PK blood and urine collection timepoints (see [Table 2](#)).

Table 4 Detailed Schedule of PK, Urine, dECG, Safety ECG, ASQ, Injection Site Assessment and Vital Signs During Single IV Administration Days -1 to Day 3

Day	Time Relative to IV Infusion Dose (T=0) ^a and PK windows	Time relative to End of Infusion ^b (EOI)	PK Blood ^b	Urine ^c	dECG ^d and Safety ECG ^e (triplicates)	Vital Signs ^f	ASQ ^g	Injection Site Assessment ^h
Admission/ Day -1	4 hour Holter*				X^{d,e} (4 hour Holter)	X^f	X	
Day 1	Predose (within 60 minutes of dose)	Predose	X (Within 60 mins of start of infusion)		-12 to 0 hr (±15 min)	X^{d,e} (Holter to start approx. 60 mins before start of infusion)	X (within 60 mins of start of infusion)	X (within 60 mins of start of infusion)
		5 minutes into Infusion				X^j (±2.5 min)		
	End of IV infusion (+1 minute)	At End of Infusion (EOI)	Xⁱ (+1 min)			X^j (1 to 4 min post EOI)		X (+15 min)
	15 min (+1 minutes)	5 minutes	Xⁱ (+1 min)					
	20 min (+1 minutes)	10 minutes	Xⁱ (±1 min)					
	30 min (+2 minutes)	20 minutes	Xⁱ (±2 min)					
	40 min (+2 minutes)	30 minutes	Xⁱ (±2 min)					
	50 min (+4 minutes)	40 minutes	Xⁱ (±4 min)					
	1 hr, 10 minutes (+4 minutes)	1 hr	Xⁱ (±4 min)					
	1 hour, 40 minutes (+10 minutes)	1.5 hr	Xⁱ (±10 min)					
	2 hr, 10 minutes (+10 minutes)	2 hr	Xⁱ (±10 min)					
	2 hr, 40 minutes (+10 minutes)	2.5 hr	Xⁱ (±10 min)					
	2 hr, 10 minutes (+10 minutes)	3 hr	Xⁱ (±10 min)		2 to 4 hr (±15 min)	X^e (±10 min)	X (±10 min)	X (+15 min)
	4 hr (+15 minutes)	4 hr	X (±15 min)					X (+15 min)
	5 hr (+15 minutes)	5 hr			4 to 6 hr (±15 min)			X (+15 min)
	6 hr (+15 minutes)	6 hr	X (±15 min)			X^e (±10 min)	X (±10 min)	X (+15 min)
	8 hr (+15 minutes)	8 hr	X (±15 min)		6 to 12 hr (±15 min)	X^e (±10 min)	X (±10 min)	
	12 hr (+15 minutes)	12 hr	X (±15 min)					
Day 2	24 hr (+30 minutes)	24 hr	X (±30 min)	12 to 24 hr (±15 min)	X^{d,e} (Holter to end after 24-hr)	X (±10 min)		X (+12 hr)
	36 hr (+30 minutes)	36 hr	X (±30 min)	24 to 36 hr (±15 min)		X (±10 min)		
Day 3	48 hr (+30 minutes)	48 hr	X (±30 min)	36 to 48 hr (±15 min)	X^e (±10 min)	X (±10 min)		X (any time prior to discharge)

Abbreviations: ASQ: Anxiety Symptoms Questionnaire; CRU = clinical research unit; dECG: Digital electrocardiogram; EOI = end of infusion; hr = hour; IV = intravenous; min = minutes; PK: pharmacokinetics; (T=0) = Time equals 0.

* Continuous Holter performed during the day of admission

- a. All predose procedures and PK blood samples may be taken up to 60 minutes prior to start of the 10 minute IV infusion on Day 1. All postdose procedures and PK blood samples will be collected relative to the end of the IV infusion unless otherwise indicated or there is a significant extension of the infusion duration (see footnote ^b below).
- b. The following windows will be allowable for PK samples: a ±1 minute window will be allowed for samples taken up to and including 10 minutes postdose, a ±2 minute window will be allowed for samples at 20 and 30 minutes postdose, a ±4 minute window will be allowed for samples at 40 minutes, 50 minutes, and 1 hour postdose, a ±10 minute window for samples taken between 1.5 hours and 3 hours postdose; a ±15 minute window is acceptable for samples taken at >3 hours postdose, and a ±30 minute window is acceptable for samples taken at >12 hours postdose.
- c. A small amount of urine will be removed at each interval for urinalysis. Removal of urine will occur after the volume of the pooled urine has been recorded.
- d. ECGs to be extracted from the continuous Holter on Days 1 and 2 as listed in [Table 2](#) and will be time-matched with PK sample collections from predose to 24-hour postdose. Digital ECG assessments will be extracted at a time prior to the PK sample collection. Participants will remain in supine position for at least 5 minutes before each of the planned ECG extraction.
- e. Scheduled safety ECG by site for in-time evaluation of ECGs. Timepoints will be from the start of the triplicate assessment as indicated. Single ECG will be collected at the 10 and 30 minutes post EOI timepoints.
- f. Vital signs can be taken any time prior to randomization on Admission/Day -1.
- g. On Day 1, ASQ will be completed predose (within 60 minutes prior to dosing) and approximately 10 minutes (+15 minutes), 1 hour (+15 minutes), and 2 hours (+15 minutes) postdose. This assessment will be performed after completion of all other simultaneously scheduled procedures to avoid interference with scheduled vital sign, ECG, and PK evaluation (see [Section 8.2.4](#)).
- h. On Day 1, the injection site will be evaluated prior to study treatment administration and again immediately after study treatment administration, in approximately hourly (+15 minutes) intervals for up to 6 hours postdose. Injection site assessment also occurs any time on Day 2, and any time prior to discharge from the CRU on Day 3 (see [Section 8.2.1.1](#) for details on the 4 point scale injection site assessment).
- i. If the duration of the short 10 minute infusion exceeds 15 minutes, or an interruption occurs that exceeds the duration of infusion to more than 15 minutes, for PK blood collection (postdose) up and including 3 hours, every effort should be made to follow the time relative to the end of infusion.
- j. Blood pressure measurements for 5 minutes post start of infusion, at EOI, and 20 minute post EOI timepoints will be single readings.

The timing of PK (both plasma and urine), safety ECG, and vital sign assessments may be adjusted based on emerging data. Furthermore, in case that CS-1103 half-life is less than 4 hours, Holter recording may be discontinued at a time earlier than 24 hours post IV infusion. Furthermore, up to 2 additional blood collections may be added on Day 1, Day 2, or Day 3; pooled urine collections may be extended, and discharge may be delayed for up to 8 hours to optimize PK assessment without preparation of an amendment.

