6.4.2 Individual Study Treatment Adjustment/Interruption

If a participant experiences a reaction symptom, the study treatment infusion should be stopped. The infusion may be restarted at a slower rate or halted entirely based on an Investigator's discretion. Any interruptions (stop time/restart time) will be documented.

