8.0 STUDY ASSESSMENTS AND PROCEDURES

- Study procedures and their timing are summarized in the SoA ([Section 1.3](#)). Protocol waivers or exemptions are not allowed.
- Immediate safety concerns should be discussed with the Sponsor immediately upon occurrence or awareness to determine if the participant should continue or discontinue study treatment.
- Adherence to the study design requirements, including those specified in the SoA ([Section 1.3](#)), is essential and required for study conduct.
- All screening evaluations must be completed and reviewed to confirm that potential participants meet all eligibility criteria. The Investigator will maintain a screening log to record details of all participants screened and to confirm eligibility or record reasons for screening failure, as applicable.
- Procedures conducted as part of the participant's routine clinical management (e.g., blood count) and obtained before signing of the informed consent form (ICF) may be utilized for screening or baseline purposes provided the procedures met the protocol-specified criteria and were performed within the timeframe defined in the SoA ([Section 1.3](#)).

The maximum amount of blood collected from each participant over the duration of the study, including any extra assessments that may be required, will not exceed 450 mL.

Repeat or unscheduled samples may be taken for safety reasons or for technical issues with the samples.

When multiple procedures are scheduled at the same visit, the order of assessments will be, ECG procedures, vital signs, PK sample collection (nominal), questionnaire, and injection site assessment. All scheduled postdose times listed for the assessments in the SoA ([Section 1.3](#)) are relative to the start of the IV infusion unless there is a significant extension of the infusion duration or infusion interruption (see [Table 2](#)).

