8.4.3 Calculation of Derivation of Pharmacokinetic Variables

Pharmacokinetic parameters will be derived using noncompartmental methods with Phoenix® WinNonlin® Version 8.3 or higher (Certara, L.P. Princeton, New Jersey, United States of America [USA]) and/or SAS® Version 9.4 or higher (SAS Institute, Inc., Cary, North Carolina, USA). Actual elapsed time from start of the IV infusion will be used for the final plasma PK parameter calculations. Nominal time from end of the IV infusion will be used for preliminary PK parameter calculations.

The plasma PK parameters in Table 4 will be determined for CS-1103. A minimum of 3 quantifiable postdose concentrations will be required for all calculations.

Table 6 Plasma Pharmacokinetic Parameters

Pharmacokinetic Parameter	Definition
C_{\max}	Maximum concentration, obtained directly from the observed concentration versus time data
C_{EOI}	Concentration at the end of the 10-minute IV infusion
t_{\max}	Time to C_{\max}
$AUC_{(0-\infty)}$	Area under the plasma concentration-time curve from time zero extrapolated to infinity, calculated by linear up/log down trapezoidal summation
$AUC_{(0-\text{last})}$	Area under the plasma concentration-time curve from time zero to the time of the last quantifiable concentration, calculated by linear up/log down trapezoidal summation
CL	Systemic clearance

V_z	Volume of distribution
V_{ss}	Steady-state volume of distribution
$t_{1/2}$	Half-life; a minimum of 3 points will be used for estimation
λ_z	Elimination rate constant

Abbreviation: IV = intravenous.

Note: No dose correction for the sodium salt will be required for dose-dependent parameters, as both CS-1103 dose and plasma concentrations will be based on the weight of the tetrasodium salt.

For this study, an extrapolation of 30% will be considered acceptable for considering $AUC_{(0-\infty)}$ sufficiently well defined. Dose normalized exposure will also be determined. Additional plasma parameters may be calculated if deemed appropriate. Further details with respect to the PK analysis will be provided in the statistical analysis plan (SAP).

Any preliminary plasma PK result for use by the SRC will be reported in a manner that maintains blinding of the treatment the participants have received unless otherwise requested by the SRC. The urine PK parameters in Table 5 will be determined for CS-1103.

Table 7 Urine Pharmacokinetic Parameters

Pharmacokinetic Parameter	Definition

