9.4 Interim Analysis

No formal interim analysis is planned. Preliminary PK parameters will be calculated using available quality-controlled CS-1103 concentrations and scheduled sampling times to support dose escalation decisions, as applicable.

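### Postdose times run from the start of infusion in two places and from the end in a third, so sampling times are unclear when the 10-minute infusion overruns

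*Protocol*

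**What the plan says.** **Start clock.** Protocol Section 1.3, Table 1 footnote n, states that all scheduled postdose assessments in Tables 1 and 2 "are relative to the start of the IV infusion", without exception. Section 8.0 repeats that they "are relative to the start of the IV infusion unless there is a significant extension of the infusion duration" or an interruption.

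**End clock.** Table 2 footnote a: "All postdose procedures and PK blood samples will be collected relative to the end of the IV infusion unless otherwise indicated". It then lifts this rule for a significant extension and sends the reader to footnote b.

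**Footnote b** lists only PK windows, including "a ±4 minute window will be allowed for samples at 40 minutes, 50 minutes, and 1 hour postdose". In Table 2, 50 minutes appears only in the start column and 1 hour only in the EOI column.

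**Footnote i** holds the working rule for long infusions. Above 15 minutes, for postdose PK blood up to 3 h, "every effort should be made to follow the time relative to the end of infusion".

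**Overruns are foreseen.** Section 6.4.2, on reactions during the infusion: "The infusion may be restarted at a slower rate".

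**Use of the times.** Section 8.4.3: "Nominal time from end of the IV infusion will be used for preliminary PK parameter calculations". Section 9.4 uses "scheduled sampling times to support dose escalation decisions", and SAP 4.1 agrees. Final parameters use actual times, from the start of infusion in Protocol 8.4.3 and from its end in SAP 15.2.

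**The concern.** Site staff hold two opposite instructions for the same draw. Whether a draw is early, on time or a deviation depends on which footnote is read. This leaves two gaps.

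1. **Infusions over 10 and up to 15 minutes.** Footnote i does not apply. A site following footnote n draws the early samples too soon after EOI, and the preliminary PK for the Safety Review Committee (SRC) then treats them as if drawn at the nominal post-EOI times. A site following footnote a makes no such error.
2. **Extended or interrupted infusions.** No consistent rule covers PK after 3 h, later safety ECGs and vital signs, or the Anxiety Symptoms Questionnaire (ASQ).

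Preliminary PK supports escalation in a first-in-human trial, and Section 4.6.1 sets an AUC(0-last) limit of 456 µg·h/mL.

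**Working it through.** **Step 1: difference between the clocks.** For an infusion of T minutes, the difference is (T + EOI label) − start label. Through 3 h the start label is the EOI label plus 10 minutes, so the difference is T − 10. (The start label printed in the 3 h row is read as 3 h 10 min and is not used as evidence.) From 4 h on, both columns print the same value, so the difference is T.

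**Step 2: compare with the PK windows.** These are ±1 minute (EOI+5, +10), ±2 (+20, +30), ±4 (+40 min, +1 h) and ±10 (1.5–3 h). In whole minutes, a start-clock draw leaves the ±1 window at T = 12, the ±2 window at 13 and the ±4 window at 15. The ±10 windows are not breached up to 15.

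**Step 3: effect on preliminary AUC (illustration).** Inputs are the projection at 40 mg/kg in the footnote to Section 4.5: C0 340 µg/mL and AUC 318 µg·h/mL. A one-compartment model is assumed, so k = 340/318 = 1.069 /h and half-life = ln 2/1.069 = 0.648 h. With total AUC A = 318 and T in hours:

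- during infusion, C(t) = (A/T)(1 − e^(−kt))
- afterwards, C(t) = (A/T)(1 − e^(−kT)) e^(−k(t−T))

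The EOI sample is at T and the others at start-column times. AUC to 12 h is by linear-up/log-down on nominal post-EOI times, compared with the same grid correctly timed.

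| T (min) | Draws through 3 h early by (min) | PK draws outside window | AUC, mistimed | AUC, correct | Excess |
|---|---|---|---|---|---|
| 10 | 0 | 0 | 292.7 | 291.3 | +0.5% |
| 11 | 1 | 0 | 295.1 | 288.8 | +2.2% |
| 12 | 2 | 2 | 297.6 | 286.3 | +4.0% |
| 13 | 3 | 4 | 300.2 | 283.9 | +5.8% |
| 14 | 4 | 4 | 302.8 | 281.4 | +7.6% |
| 15 | 5 | 6 | 305.4 | 279.0 | +9.4% |

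The +0.5% at exactly 10 minutes comes from the identical labels at 4 h and later, not from an overrun. At T = 15 the start-clock 15-minute draw coincides with the EOI draw (both 298.4 µg/mL), which staff would probably notice.

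**Step 4: other half-lives, total AUC held at 318.**

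| Half-life | T = 10 | T = 12 | T = 15 |
|---|---|---|---|
| 0.5 h | +0.2% | +4.7% | +11.8% |
| 1 h | +1.1% | +3.4% | +6.9% |
| 2 h | +1.7% | +2.9% | +4.6% |

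**Step 5: compare with total exposure and the limit (base case).** For T = 12 to 15, mistimed values are 6.4% to 4.0% below 318. Correctly timed post-EOI values are 10.0% to 12.2% below, because they omit the infusion phase. Start-clock actual times with the infusion phase included give 316–317 for T = 10 to 15. The highest mistimed value is 305.4/456 = 67% of the limit.

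**Step 6: later readings.** From 4 h the clocks differ by T. An ECG or vital-sign reading with a ±10 minute window that is exactly on time on one clock is outside on the other once T exceeds 10. For PK at 4–12 h (±15) this happens once T exceeds 15, and for PK at 24–48 h (±30) once T exceeds 30. If ASQ is due 10 to 25 minutes postdose, the first start-clock window is 10–25 minutes and the first end-clock window is T+10 to T+25. They overlap by 5 minutes at T = 10 and not at all from T = 15. The pharmacological effect is small: 6 h is 6/0.648 = 9.3 half-lives, and e^(−1.069×3) = 4.0% of post-EOI AUC lies after 3 h.

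**The case against.** **The text can be read as one scheme.** Footnote n, Section 8.0 and footnote i fit together as a start clock by default and an end clock above 15 minutes; footnote i would be unnecessary if the end clock were already the default. Footnote a is then the outlier. This is a fair reading, and it means a start clock is a legitimate repair. It does not remove the problem. If the words on other indications in footnote a defer to footnote n, footnote a governs nothing, and start-clock draws still receive end-clock labels under Section 8.4.3.

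**Section 8.0 partly covers long infusions.** It drops the start clock for all assessments and points to Table 2, which has an EOI column. But footnote a suspends the end clock in the same situation, and footnote i stops at PK blood to 3 h. Some ambiguity remains. Footnotes e and j do tie a few early ECG and blood pressure readings to EOI, so those are clear.

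**The consequences are limited.** Infusion start and end times (Section 6.4) and actual sample times (Section 8.4.1) are recorded. SAP 11.1 lists deviations and SAP 15.1 lists sampling-time deviations. ASQ is only listed (SAP 16.8). All of this stands and sets the severity.

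**An end clock for everything would not correct the AUC.** This also stands. Correctly timed post-EOI values are further below total exposure than the mistimed ones, so the area during infusion has to be added whichever clock is chosen.

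**Conclusion.** The contradiction is in the current text and should be removed, as a minor consistency correction. For overruns of 10 to 15 minutes the preliminary post-EOI AUC could be overstated by about 3–5% at 12 minutes and 5–12% at 15, including 0.2–1.7% that is present even at 10 minutes. This assumes that the site follows the start clock and that kinetics are one-compartment with a half-life of 0.5 to 2 h. The documents give no frequency of overruns. For later readings the effect is on window compliance and comparability.

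A reader might infer three stronger things that the documents do not support:

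- **That mistimed draws could hide a breach of the 456 limit.** The error raises AUC. Any shortfall against total exposure comes from leaving out the infusion phase, not from the clock conflict.
- **That ordinary 10-minute infusions yield mistimed early samples.** For exactly 10 minutes the two clocks agree through 3 h, with the 3 h row read as above.
- **That the final PK is affected in the same way.** Both documents use actual times for it.

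The number of later ECG and vital-sign readings affected is not stated here, because Table 2 is too broken in the available text to count them reliably.

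**What to change.** 1. **One default clock.** State it identically in Table 1 footnote n, Table 2 footnote a and Section 8.0; start or end will both do. Delete footnote a's reversed exception and cite footnote i instead of b.
2. **Long infusions.** Add one sentence extending footnote i's rule to PK after 3 h, safety ECG, vital signs and ASQ. Write footnote b's windows on the chosen clock only.
3. **Preliminary PK (Protocol 8.4.3 and 9.4, SAP 4.1).** When a participant's infusion length puts any PK sample outside its window (in whole minutes, 12 or more) or the infusion was interrupted, calculate from recorded sample times and recorded infusion start and end. Include the infusion-phase area in AUC(0-last) before comparison with 456 µg·h/mL. Keep scheduled times otherwise.

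**Cost.** Wording changes in the protocol, SAP 4.1 and site worksheets. No new procedure is needed, since the times are already recorded. The downside is a check of recorded times for the affected participants before each SRC review.
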